Two pilot studies^{61,62} found that combining SDT-based MI interventions with wearable tracker use significantly improved self-reported PA, body weight, and HDL cholesterol in African American men⁶¹ and increased the likelihood of meeting daily step goals in adolescent-parent dyads.⁶² These results present an encouraging possibility for improving PA in sedentary adults: WFTs and SDT based MI. Given the popularity of wearable fitness trackers and the effectiveness of SDT based MI in increasing PA motivation and behavior, the combination of the two shows promise to improve the overall health of adults. Therefore, the purpose of this study is to assess the impact of a self-determination theory motivational interviewing intervention in combination with wearable fitness tracker use on motivation for PA and PA behavior.

Methods

Participant Recruitment and Health Screening

Participants aged 18 and over will be recruited through a variety of means including flyers on the Colorado State University campus, flyers in local fitness centers, physician referrals, social media, and mass emails. In order to detect difference between groups with 95% confidence in repeated measures analyses, we will seek to recruit 40 total participants in order to allow for attrition. We aim to have 32 participants complete the study. To be included in this

study, participants must be over the age of 18 and must not meet physical activity guidelines of at least 150 minutes of moderate physical activity per week. They must own an Android or iPhone smartphone device and be willing to download a mobile application onto that device for use during the intervention. They also must be willing to potentially wear a WFT and/or attend bi-weekly remote MI. Participants must not have a history of heart disease or diabetes, and must not have limiting conditions like concurrent cancer treatment, peripheral artery disease, orthopedic injury, or pain limiting arthritis. They must also not seek to participate in other structured PA programs for the duration of the study, must not be pregnant or seek to become pregnant, and must not have been diagnosed with alcohol or substance abuse during the previous twelve months.

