After having established the eligibility of a potential participant via a screening form, participants will be consented and will complete baseline assessments. This session will involve the administration of all self-reported measures, as well as instruction on accelerometer use. Participants will wear the accelerometer for the subsequent 7 days to provide baseline data on their baseline level of PA. Researchers will collect the ActiGraphs after the 7-day period.

Participants who complete the baseline PA assessment will be invited to a remote session to receive general physical activity guidelines education and will take approximately 1 hour. Prior to this meeting, participants will have been randomly assigned to one of the four study groups (i.e., WFT, MI, WFT+MI, or PA Education Control) using a randomized number generator. To control for age and sex, participants will be age- and sex-matched in each group. During this remote meeting, participants will be informed as to which group they have been randomized into.

Description of Intervention:

The duration of the study will be twelve weeks. The four study conditions are as follows:

WFT: Individuals assigned to this experimental condition will be given a wrist-worn WFT and will be instructed to wear it for the duration of the study. They will also be instructed to download the corresponding mobile application on their smartphones to be used for the duration of the study. They will be trained by a member of our team on how to utilize the WFT and mobile application. The intended WFT tracks daily steps, miles traveled, kcals expended, and daily activity time. This device provides these data to the wearer via a small screen. Participants will be instructed to try and complete at least 150 minutes of PA per week. Researchers will have the capability to track participant daily PA via the WFT mobile application account created for each participant. These individuals will be asked to set biweekly PA goals, which will be emailed to the study coordinator. These participants will also receive general physical activity guidelines education and information on strategies to reach the recommended amount of activity per week during the initial baseline assessment meeting. Participants in this condition will be asked to ONLY wear the WFT provided to them by researchers.

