- **Objectively measured PA engagement:** PA will be objectively measured by one week of actigraphy using the ActiGraph wGT3-BT activity monitor. Participants will be given the ActiGraph and will be instructed to wear it on a provided elastic belt on their non-dominant hip for one week. They will be given a log to record times that they removed the ActiGraph, which should only be when showering, bathing, or otherwise coming into contact with water. At the conclusion of the week, the ActiGraph data will be downloaded using ActivLife software. Daily PA will be assessed via the WFT

application for individuals in the WFT+MI and WFT groups, and via self-report for the MI group.

- **Motivation for PA:** Motivation for PA will be assessed using the Behavioral Regulation in Exercise Questionnaire (BREQ-3). This instrument is one of the most widely used in PA and exercise motivation research and has been validated in this population.^{21,22} This survey will be accessed via a secure online link.
- **Covariates:** Each of the following covariates will be collected pre-intervention: age, race/ethnicity, education level, family affluence, and height/weight (BMI). All, except height and weight will be collected with self-report. Height and weight will be measured by lab personnel during the first visit to the lab.

Data Analysis

Means and standard deviations of the following variables will be calculated: baseline and follow-up MVPA, steps, and energy expenditure, baseline and follow-up scores for PA motivation subscales, and participant age and BMI. Paired t-tests will be used to compare within subjects pre-participation values from post-participation values for PA, and motivation variables by group. ANCOVA will be used to compare between subjects differences in outcome variables by group. Models will be developed based on covariate correlation with outcome variables and other covariates.

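### The plan does not say that conclusions rest on the between-group ANCOVA rather than the within-arm paired t-tests, and it does not guarantee baseline adjustment in that ANCOVA.

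*Combined protocol and SAP*

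**What the plan says.** The inferential plan is three sentences in the Data Analysis section. The first sets up within-arm tests: "Paired t-tests will be used to compare within subjects pre-participation values from post-participation values for PA, and motivation variables by group". Outcomes are taken at baseline and at twelve weeks in all four groups, so these tests cover WFT, MI, WFT+MI and the education control. The second sentence is the between-group analysis: "ANCOVA will be used to compare between subjects differences in outcome variables by group". The third is the rule for building the model: "Models will be developed based on covariate correlation with outcome variables and other covariates".

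The Covariates item under Outcome measures reads: "Each of the following covariates will be collected pre-intervention: age, race/ethnicity, education level, family affluence, and height/weight (BMI"). The baseline value of the outcome is not in that list.

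Two other places bear on intent. Under Participant Recruitment and Health Screening, the sample size is justified by the words "In order to detect difference between groups with 95% confidence in repeated measures analyses", followed by "We aim to have 32 participants complete the study". At the end of the Background, "the purpose of this study is to assess the impact of a self-determination theory motivational interviewing intervention in combination with wearable fitness tracker use", with no comparator named.

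No sentence ranks the paired tests against the ANCOVA, names a contrast or reference arm, or says whether the baseline outcome is always in the model.

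**The concern.** The paired tests and the ANCOVA answer different questions. A paired test asks whether one arm changed. It cannot say why, because all four arms receive the same activity education and an arm can also change with time or repeat measurement. Only a comparison between randomised arms isolates the contribution of WFT or MI.

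The risk is in how the results are read. With small arms, one active arm will often cross 0.05 while control does not, even when all arms have moved by the same amount. If the plan does not say beforehand that this pattern is descriptive, it can be reported as evidence of efficacy. The sample-size sentence shows that a between-group question is intended, but it refers to repeated measures analyses, and the Data Analysis section specifies no between-group repeated measures model. The reader therefore cannot tell from the text which result is meant to answer the question.

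The second issue is the covariate rule. In a two-timepoint design the baseline value is usually the most useful covariate, and it is already collected. Whether it enters here depends on correlations seen in the data, if it is a candidate at all.

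**Working it through.** **Inputs from the documents.** Four arms, 40 recruited, 32 completers, 95% confidence. The planned attrition is 1 − 32/40 = 20%, and 32/0.80 = 40, so that step is consistent. The figure of 32 cannot itself be reproduced, because no power, effect size, SD or pre-post correlation is given. Nothing below depends on it beyond arm size.

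**Assumptions.** Equal arms (32/4 = 8 completers each), two-sided 0.05, one normally distributed outcome, the same true change in every arm (no effect of WFT or MI), and arms independent. Changes are in SDs of the change score.

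**Step 1: one arm.** The paired t-test has n = 8, 7 df and critical value 2.365. The chance u of a significant improvement is the upper-tail probability of a noncentral t with noncentrality d√8, where d is the common change.

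**Step 2: the pattern.** At least one of three active arms improves significantly and control does not: (1 − u)(1 − (1 − u)³). For WFT+MI alone against control: u(1 − u).

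| Common change d | u | At least one active arm, not control | WFT+MI, not control |
|---|---|---|---|
| 0 | 0.025 | 0.071 | 0.024 |
| 0.25 | 0.089 | 0.223 | 0.081 |
| 0.5 | 0.231 | 0.420 | 0.178 |
| 0.75 | 0.449 | 0.459 | 0.247 |
| 1.0 | 0.681 | 0.309 | 0.217 |

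Worked case, d = 0.5: (1 − 0.231)(1 − 0.769³) = 0.769 × 0.545 = 0.42.

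The table counts improvements only. Counting significant declines as well would give 14% and 5% in the first row (p = 0.05 per arm: 0.95 × (1 − 0.95³) = 0.136 and 0.05 × 0.95 = 0.048). From 0.5 SD upward, direction makes almost no difference.

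**Step 3: the direct comparison.** In simulation of an ANCOVA with baseline fixed in advance (4 arms of 8, correlations 0.3 to 0.7, equal true change), the WFT+MI v control test rejected in 4.9 to 5.1% of trials. This describes the model recommended below, not the correlation-driven model in the plan, which is not specified closely enough to simulate.

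**Step 4: what baseline adjustment could be worth.** Let r be the correlation between the baseline and 12-week values; the documents give none. In SDs of the 12-week value, the standard error of an 8 v 8 contrast is √(1 − r²) × √(2/8). With no covariate it is 0.500 on 28 df, and the difference detectable with 80% power is 1.45 SD. With baseline in the model (27 df):

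| Assumed r | Standard error | Detectable difference |
|---|---|---|
| 0.3 | 0.477 | 1.39 SD |
| 0.5 | 0.433 | 1.26 SD |
| 0.7 | 0.357 | 1.04 SD |

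The covariate-free comparator is the extreme case. It applies only if the selection rule left baseline out and no other covariate took up part of its role.

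**The case against.** The strongest reply is that the plan already contains the right test. It assigns between-subject differences to an ANCOVA and ties its sample size to differences between groups. Reporting pre-post tests beside a between-group test is common, and nothing says that efficacy will be read from them. This stands in full against one reading that a reader might infer, namely that the plan will base its conclusions on the paired t-tests. The documents do not say so. What they lack is a statement that it will not, and the t-tests are presented as comparisons, apart from the means and standard deviations.

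The second reply concerns baseline. A reader might infer that the plan omits it and so throws away precision. The text does not support that. The Covariates item lists extra variables to be gathered, baseline outcomes are collected elsewhere as outcome measures, ANCOVA in a pre-post design often means baseline adjustment, and a rule based on correlation with the outcome might well select it. What remains is that inclusion is left open and, under the stated rule, would depend on the data.

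Third, the percentages in Step 2 describe a decision rule that the plan never adopts. This is correct, and they should not be quoted as type I error rates of the trial. The peak of 46% also needs a common improvement of about 0.75 SD in every arm, including control, and counts any of three active arms.

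Finally, regression to the mean should not be pressed. Eligibility is set "After having established the eligibility of a potential participant via a screening form", not by the baseline accelerometer reading, so its contribution to within-arm change is limited.

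**Conclusion.** The point holds as a gap in specification that can be closed at almost no cost. The plan contains a between-group test but does not make it the basis for conclusions, and it does not guarantee adjustment for the baseline outcome.

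If within-arm results were read as evidence of efficacy, the misleading pattern would appear in about 7 to 46% of trials across common changes of 0 to 1.0 SD, or about 2 to 25% for WFT+MI alone. This assumes 8 completers per arm, a single outcome and equal true change in all arms.

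The gain in precision is conditional. At an assumed correlation of 0.5, the detectable difference falls from 1.45 to 1.26 SD only if baseline would otherwise have been left out and not replaced. If the selection rule would have included it anyway, precision does not change, and the benefit is protection from a data-driven choice.

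**What to change.** In the Data Analysis section, state:

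1. The ANCOVA of the 12-week value always includes the baseline value of the same outcome, fixed in advance and exempt from the correlation-based selection.
2. Conclusions about WFT and MI rest on this between-group ANCOVA. Within-arm changes are reported as mean change with 95% CI and labelled descriptive.

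The sponsor should also name the between-group contrast that matches its stated purpose. The purpose sentence gives no comparator, so which contrast to use (for example WFT+MI against control, or the WFT and MI main effects), and any scheme for handling several, is the sponsor's choice. The sample-size sentence should then refer to the same analysis.

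Cost: no new data, one degree of freedom for the baseline term, and within-arm p-values are no longer used as evidence of efficacy. The change does not make 8 v 8 contrasts precise, and it does not settle multiplicity across MVPA, steps, energy expenditure and the motivation subscales.

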Multiple Behavior Change Techniques Are Better Than One

One potential method to improve the effectiveness of WFTs is to combine them with other interventions. According to a review by Sullivan and Lachman,¹³ the most effective strategy to increase PA and sustain that increase is to employ multiple behavior change techniques. Several studies have combined wearable tracker use with other interventions such as cash incentives for hitting goals,⁴⁸ challenges sent to participants via email,⁴⁷ and a mobile application loaded with an exercise program.⁴⁴ Specifically, we propose combining WFT use with a Self-Determination theory driven Motivational Interviewing (MI) intervention to improve PA motivation and engagement.

Motivational Interviewing and Physical Activity

MI is a person-centered form of engagement that encourages people to assess their own position on the motivation continuum, explore the reasons behind their position, and determine how to best shift from amotivation or ambivalence to a more autonomous position. While MI was not developed with SDT in mind, Deci & Ryan⁵³ point out that SDT and MI have historically been congruent, particularly with their emphases on autonomy support to make health-related decisions and changes. Specifically, both SDT and MI are focused on the central ideal of motivation and the development of internal motives, and the exposure and consideration of externally imposed goals or pressures to act which have no personal meaning to the

individual.⁵⁴ SDT constructs and MI, both on their own and combined, are effective in improving both motivation for PA and PA behavior in a range of age groups. A number of studies measuring changes in PA in response to an SDT-based intervention or MI, or a combination of the two saw statistically significant increases in PA.^{39,43,55-58} Research has also indicated that SDT-based MI is a powerful intervention to shift motivation for PA from mostly extrinsic to mostly intrinsic.^{39,59,60}

WFTs and MI: A Powerful Combination

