MI: The individuals will be scheduled for and participate in six biweekly remote SDT based MI sessions. These sessions will take place via video calling platforms like Microsoft Teams, Zoom, or Skype. The MI sessions will be conducted by a PhD student who has been trained by a MI practitioner. Participants will be provided a log book and will be asked to log their PA, with the goal of completing at least 150 minutes of PA per week. These participants will also receive general physical activity guidelines education and information on strategies to reach the recommended amount of activity per week during the initial baseline assessment meeting. Participants in this condition will be asked to NOT wear a WFT of their own over the course of the intervention.

WFT+MI: These individuals will be given the wrist-worn WFT, be instructed to wear it for the duration of the study AND be scheduled for six SDT based remote MI sessions. These participants will also be trained by a member of our team on how to utilize the WFT and associated application. They will be instructed to try to complete 150 minutes of PA per week. Researchers will have the capability to track participant daily PA via the WFT and associated API. These participants will also receive general physical activity guidelines education and information on strategies to reach the recommended amount of activity per week during the initial baseline assessment meeting. Participants in this condition will be asked to ONLY wear the WFT provided to them by researchers.

PA Education Control: These participants will receive general physical activity guidelines education and information on strategies to reach the recommended amount of activity per week during the initial baseline assessment meeting. Participants will be asked to NOT wear a WFT of their own over the course of the intervention. At the conclusion of the study, these participants will be offered the chance to participate in one MI session.

Outcome measures: The following outcome measures will be collected at baseline, and at the completion of the twelve-week intervention.

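### The stated purpose is MI combined with a tracker, but the plan names neither the between-group contrast that decides it nor a primary outcome

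*Combined protocol and SAP*

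**What the plan says.** The background section on multiple behavior change techniques gives the rationale: "One potential method to improve the effectiveness of WFTs is to combine them with other interventions". The section on combining WFTs and MI then states that "the purpose of this study is to assess the impact of a self-determination theory motivational interviewing intervention in combination with wearable fitness tracker use", with motivation and activity behavior as the targets. It names no comparator.

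Four arms are randomized: WFT, MI, WFT+MI and PA Education Control, a 2x2 layout. The recruitment section adds: "To control for age and sex, participants will be age- and sex-matched in each group". It aims for 40 recruited and 32 completers.

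Data Analysis contains two kinds of test. The first is within group: "Paired t-tests will be used to compare within subjects pre-participation values from post-participation values for PA, and motivation variables by group". The second is between groups: "ANCOVA will be used to compare between subjects differences in outcome variables by group". Covariates are to be chosen from their correlations with the outcomes and with each other. The variables to be summarized are "baseline and follow-up MVPA, steps, and energy expenditure, baseline and follow-up scores for PA motivation subscales" (plus age and BMI), with no ranking of the outcomes.

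The arm descriptions differ in more than tracker and MI. Under WFT only: "These individuals will be asked to set biweekly PA goals, which will be emailed to the study coordinator". Under MI only: "Participants will be provided a log book and will be asked to log their PA".

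**The concern.** The purpose is about a combination, so the answer depends on what the combination is compared with. WFT+MI minus WFT asks what MI adds to a tracker, which is the question the rationale raises. WFT+MI minus MI asks what a tracker adds to MI. WFT+MI minus control asks whether the package does anything. The interaction asks whether the effects are more than additive. These can give different answers in the same data, and the plan designates none of them.

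The paired t-tests have no comparator, so they cannot separate an intervention effect from change that would have occurred anyway. An overall test of group, if that is what the ANCOVA sentence means, says only that some arm differs from some other.

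Two things are at stake. One is modest error inflation if several contrasts are examined and one is emphasized. The other, and larger, is misattribution: a true tracker effect could be reported as evidence that MI improves on the tracker.

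**Working it through.** **The plan's own figure.** The 32 completers cannot be reproduced, because no effect size, SD, power or target contrast is given. The recruitment step is consistent (32 / 0.80 = 40), but the 20% loss is itself implied by 32/40, so this checks nothing.

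**Inputs.** From the documents: four arms, 32 completers, 40 recruited, 95% confidence. Assumed: equal arms (32/4 = 8 each), two-sided 0.05, baseline to follow-up correlation r = 0.5 (range 0 to 0.7), and an illustrative effect of 0.8 SD. The model is four arms plus baseline, age and sex, so error df = 32 − 7 = 25, with critical t = 2.06. Residual variance is 1 − r² = 0.75 in outcome-SD units.

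**Precision.**
- One contrast: SE = √(0.75 × 2/8) = 0.433. The 95% CI half-width is 2.06 × 0.433 = 0.89 SD. The effect detectable with 80% power (noncentral t) is 1.26 SD (1.46 at r = 0, 1.04 at r = 0.7; 1.12 if all 40 are analyzed at r = 0.5).
- Interaction: SE = √(0.75 × 4/8) = 0.612, half-width 1.26 SD, detectable effect 1.79 SD (2.06 at r = 0, 1.47 at r = 0.7).

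**No effects at all** (simulation, one outcome, unadjusted, either direction). These rates do not depend on r.

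| Rule | At least one significant |
|---|---|
| Three WFT+MI contrasts | about 12% |
| Those three plus the interaction | 14% |
| The same four, only after a significant overall F | 4.5% |

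**Tracker gives 0.8 SD, MI adds nothing.** True means (control, WFT, MI, WFT+MI) = (0, 0.8, 0, 0.8). For the contrasts with MI and with control, the noncentrality is 0.8/0.433 = 1.85.

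| Contrast | True difference | Significant in favor of WFT+MI |
|---|---|---|
| WFT+MI minus control | 0.8 SD | 43% |
| WFT+MI minus MI | 0.8 SD | 43% |
| WFT+MI minus WFT | 0 | 2.5% |
| Both component contrasts | – | 2.2% |

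At least one of the three contrasts favors WFT+MI in 58% of such trials (48% at r = 0, 73% at r = 0.7), or in 44% if a significant F is required first.

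**Overall F test.** The noncentrality is 8 × Σ(mean − grand mean)² / 0.75.
- Only WFT+MI shifts by 0.8 SD: the sum is 3 × 0.2² + 0.6² = 0.48, giving 5.12.
- All three active arms shift by 0.8 SD: the sum is 0.6² + 3 × 0.2² = 0.48, again 5.12.

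Power is 39% in both cases, so with equal arms the test cannot tell them apart. The exact tie needs equal arms: with 10/8/8/6 it is 32% against 44%.

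**Power of a named rule when WFT+MI truly exceeds each component by 0.8 SD.** The single contrast WFT+MI minus WFT has 43%. Requiring WFT+MI minus MI as well has 27% (19% at r = 0, 42% at r = 0.7; 36% if 40 are analyzed at r = 0.5).

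**The case against.** The strongest reply is that the plan is silent, not wrong. Every WFT+MI contrast can be estimated from the four-arm ANCOVA, and nothing says that the contrast will be picked after the data are seen. That stands. A reader might infer a planned post hoc choice, but the documents support only that the choice is left open.

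A reader might also take the 58% as a false-positive rate. It is not. In that scenario WFT+MI really does exceed MI and control, and almost all of the figure (0.583 of 0.584) is power to detect those two true differences. The false statement, that WFT+MI beats WFT, arises in 2.5%. Harm follows only if a true contrast is reported as showing that MI adds something, and the plan does not say that it will be. Error inflation under no effects is modest for one outcome, and a preliminary F test would largely remove it, although the plan does not mention one.

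The log book should not be read simply as an extra intervention in the MI arm. The outcome section says daily activity comes from the tracker application in the two tracker arms and from self-report in the MI arm, so the log may stand in for tracker data. The 150-minute target is stated for all three active arms. The written difference is therefore narrower: emailed biweekly goals under WFT only, and a log under MI only.

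Finally, the effect size, correlation and equal allocation are assumptions. The gap itself rests on none of them.

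**Conclusion.** The point holds as one of non-specification. The Data Analysis section does not say which comparison answers the stated purpose, on which outcome or with which fixed covariates, and the analyses it does name do not isolate what the combination adds. Under the stated assumptions, leaving the contrast open allows about a 12% chance per outcome of a significant WFT+MI contrast when nothing works (14% with the interaction). It also allows a tracker effect to be credited to the combination: 43% for each of two true contrasts, against 2.5% for the one that tests whether MI adds to the tracker. Unranked outcomes and correlation-driven covariates widen the choice further. The documents do not support saying that the sponsor intends a post hoc choice, or that the ANCOVA cannot estimate the right contrast.

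**What to change.** 1. Name one primary outcome, such as ActiGraph MVPA.
2. Fix the model in advance, in place of selection by correlation: follow-up value on arm, baseline value, age and sex. Age and sex belong because arms are matched on them. Sex is not in the covariate list, so state that it is recorded.
3. Name WFT+MI minus WFT as the primary contrast, since it matches the rationale. Claim that the combination beats both components only if WFT+MI minus MI is also significant at 0.05. Do not let either contrast alone carry the claim under a Holm correction: in the tracker-only scenario Holm still rejects at least one of the two in about 33% of trials. If Holm is kept, state that a significant WFT+MI minus MI shows only a tracker contribution.
4. Report WFT+MI minus control, the interaction and the other outcomes as secondary estimates with 95% CIs.
5. Reconcile the arm descriptions on biweekly emailed goals and the log book, or state the difference as a limit on the contrasts.

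Items 1 to 4 are analysis wording, using data that the trial mostly already collects. Item 5 may change the arm descriptions. Precision stays low, as the detectable effects above show, and requiring both contrasts lowers power at 0.8 SD from 43% to 27%. Motivation, which the purpose also names, becomes secondary if MVPA is primary.

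### Covariate correlations choose the terms of the between-group ANCOVA, and neither the baseline outcome nor sex is fixed in it; one prespecified model should replace the rule

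*Combined protocol and SAP*

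**What the plan says.** The Data Analysis section gives one between-group method: "ANCOVA will be used to compare between subjects differences in outcome variables by group". The next sentence sets its content: "Models will be developed based on covariate correlation with outcome variables and other covariates". It gives no threshold, order of entry or fixed term, and does not say which data supply the correlations; the trial's own data are the likely source.

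Under Outcome measures, "The following outcome measures will be collected at baseline, and at the completion of the twelve-week intervention". Apart from descriptive statistics, the only stated use of the baseline values is within groups: "Paired t-tests will be used to compare within subjects pre-participation values from post-participation values for PA, and motivation variables by group".

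The Covariates entry lists five items: age, BMI, race or ethnicity, education and family affluence. Neither sex nor the baseline outcome is among them. The allocation paragraph says "To control for age and sex, participants will be age- and sex-matched in each group".

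On size, Participant Recruitment and Health Screening says "We aim to have 32 participants complete the study", from 40 recruited. The same paragraph ties the sample size to repeated-measures analyses between groups, but Data Analysis specifies no such model.

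**The concern.** Four between-group models fit the wording:

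- **A.** Baseline unused; the listed covariates are screened.
- **B.** Change scores are compared.
- **C.** Baseline is screened as one more candidate.
- **D.** Baseline is always in, as ANCOVA usually implies, and the screen chooses only extra covariates.

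Two competent analysts could fit different models to the same data, and different models to MVPA, steps, energy expenditure and each motivation subscale. The list cannot bring in sex, although the design sets out to control for it. With 32 completers in four groups, the baseline value is the main source of precision that needs no extra participants, so whether it is in the model should not be left open.

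**Working it through.** **The plan's own figure.** 40 recruited and 32 completing imply 1 − 32/40 = 20% dropout, and 32/(1 − 0.20) = 40. This is not an independent check, because the 20% is derived from the same two numbers. The 32 cannot be reproduced: no power, effect size, SD or correlation is given.

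**Inputs.** From the documents: 4 groups, 32 completers, five listed covariates, and 95% confidence read as a 5% test. Assumed: 8 completers per arm; effects over control of 0.5, 0.5 and 1.0 SD; omnibus F test; baseline-follow-up correlation r = 0.3, 0.5 or 0.7; listed covariates unrelated to outcome; screening at p < 0.05.

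**Noncentral F, ignoring chance imbalance.** The group means are 0, 0.5, 0.5 and 1.0, with mean 0.5, so λ = 8 × (0.25 + 0 + 0 + 0.25) = 4.

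- Unadjusted, df 3 and 28: power 31.6%.
- Baseline only, λ = 4/(1 − r²) = 4.40, 5.33, 7.84, df 3 and 27: 34.3, 41.0, 57.5%.
- Change score, λ = 4/[2(1 − r)] = 2.86, 4.00, 6.67, df 3 and 28: 23.2, 31.6, 50.3%.

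**Simulation including the screen** (20,000 trials per setting, Monte Carlo SE about 0.35 points). Each cell is power in %, with age and sex balanced by chance / exactly matched in sets of four.

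| Model | r = 0.3 | r = 0.5 | r = 0.7 |
|---|---|---|---|
| A: baseline unused | 30.2 / 30.9 | 30.5 / 30.7 | 30.2 / 30.7 |
| B: change score | 23.3 / 23.5 | 31.7 / 31.2 | 50.1 / 50.5 |
| C: baseline screened | 30.8 / 31.1 | 37.0 / 37.1 | 53.9 / 54.9 |
| D: baseline fixed, others screened | 31.9 / 32.2 | 38.4 / 38.7 | 54.1 / 55.1 |
| Baseline alone | 33.2 / 32.9 | 39.9 / 39.6 | 55.5 / 56.2 |
| Proposed: baseline + age + sex | 30.9 / 32.5 | 37.0 / 38.8 | 52.0 / 55.5 |

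Subtracting row by row, the proposed model gains:

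- over A, about 1-2, 6-8 and 22-25 points at the three correlations;
- over B, 8-9, 5-8 and 2-5 points;
- over C, between −2 and +2 points;
- over D, between −2 and +0.4 points.

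**If age and sex predict the outcome.** Suppose they explain 10% of the follow-up variance left after baseline. With exact matching, D has power 32.4/38.7/54.9% and the proposed model 36.9/43.5/60.5%, a gain of about 5-6 points. D's type I error is then 3.8-4.2%, against 4.7-5.2% for the proposed model. With chance balance the power gain is roughly 3 points.

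**If another listed covariate predicts the outcome.** With one such covariate (BMI, say) explaining 10% of that variance and chance balance, the proposed model loses about 0-4 points to D. At a 20% share it loses 5-6 (36/42/59% for D against 31/37/53%).

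**Type I error.** With age and sex unrelated to outcome, every single rule stays at 4.6-5.3%. Taking the smaller p-value of two models (unadjusted, baseline-adjusted) gives 6.5-8.6%. The five covariates allow 2⁵ = 32 models per outcome; taking the most favourable of them gives about 10%.

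**The case against.** The strongest reply is that ANCOVA in a pre-post design ordinarily means adjustment for baseline, and that repeated-measures analyses, named in the sample-size sentence, use baseline. This makes A the least natural model, and A supplies the 22-25 point figure. Under C or D the power case largely disappears. This stands: the documents do not support a flat statement that the plan discards baseline. They support only that no sentence settles the question.

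A reader might also infer that screening on correlations inflates type I error. It does not: a single mechanical rule stays near 5%. Higher figures require choosing a model by its result, which the wording does not plan, though it does not prevent it.

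The age and sex terms are open to challenge. With chance balance and no relation to outcome, baseline alone beats the proposed model by 2-3.5 points. The conservative type I error under D needs exact matching among completers, which is unlikely. The allocation paragraph describes no matched sets of four, and if ten sets were formed with 20% independent dropout (assumed), only about 10 × 0.8⁴ ≈ 4 would stay intact. The case for these terms is that the analysis should reflect the factors the design controls, not that they are sure to add power.

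Nor does the absence of sex from the list show bias. Sex is handled by design, and matching requires that it be recorded.

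**Conclusion.** The concern holds in a limited form. The content of the between-group model is left to covariate correlations, the baseline outcome is not fixed in it, and the stated list cannot supply one of the two matching factors. If baseline would be unused or entered only through change scores, a fixed model recovers power that the trial can ill spare. If baseline is already included or screened in, the power gain is about nil unless age and sex predict the outcome. Under every interpretation there remains the benefit of one model shared by all outcomes and fixed before results are seen. All power figures rest on assumed effects, correlations and equal arms, because the documents give none. In none of the settings simulated with the assumed effects does the proposed model reach 80% power.

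**What to change.** Replace the selection sentence with one prespecified ANCOVA for every outcome: follow-up value = baseline value of the same outcome + group + age + sex. Put any other covariates in a single, labelled sensitivity analysis. Add sex to the recorded covariates, and align the repeated-measures wording in the sample-size sentence with this model.

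The change needs SAP wording and the recording of sex, with no added participants or visits. It uses up to three error degrees of freedom (28 falls to 25 with 32 completers). If age and sex are unrelated to outcome, including them costs 0.4-0.8 points of power under exact matching and 2-3.5 under chance balance. If baseline is also uninformative (r = 0), power is 28-30% against about 31.5% unadjusted. Against a screen, the fixed model can lose a few points when another listed covariate is the strong predictor.
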